9.4 Secondary endpoints

Time from randomization to donor site healing will be compared between treatment groups using time to event approach via Kaplan-Meier (KM) method. The log-rank test will be used to compare the KM curves. Adverse events will be summarized between groups using counts and percentages. Percent of patients healed, percent use of narcotics and other pain medication (ie amount of medication used) and percent of granulation will be compared between groups using Fisher's exact test.

All analyses will be performed using SAS version 9.4 for Windows (SAS Institute Inc.). Nominal $P<$ values will be presented.

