Endpoint	The primary endpoint of this feasibility study is to evaluate if using Promogran in addition to SOC is associated with a clinically meaningful difference in pain score (≥ 2 points on the visual analog pain scale) between the treatment and control arms on postoperative day (POD) 1.
Study Duration	Two years
Participant Duration	Six weeks
Duration of IP administration	One application
Population	Twenty patients; 10 in the intervention group and 10 in the control group. All genders, ≥ 18 years old, all demographics and geographic locations; scheduled to undergo STSG.
Study Sites	Single site: NYU Winthrop Hospital
Number of participants	20 participants
Study compensation	\$70. Two payments of \$35 will be given to participants – one at enrollment and one at collection of the 10-day pain diary.
Description of Study Agent/Procedure	Promogran Prisma™ is a composite collagen-silver-oxidized regenerated cellulose dressing that is a sheet applied topically to the STSG donor site.
Reference Therapy	The control group will receive a standard of care dressing on the STSG donor site (i.e., non-adherent dressing)
Key Procedures	Placement of either Prisma or standard of care dressing on the STSG donor site. Record daily pain score of the donor site for 10 days post-grafting. Return to clinic for weekly follow-up visits for 6 weeks.

Statistical Analysis	Proposed sample size (10 patients in each arm, a total of N=20) is obtained from a recruitment and cost feasibility point of view. For the primary endpoint, the pain score at POD 1 will be compared between treatment groups using Wilcoxon rank-sum (Mann-Whitney) test. The secondary endpoint, time from randomization to donor site healing, will be compared between treatment groups using time to event approach via Kaplan-Meier method.
----------------------	--

SCHEMATIC OF STUDY DESIGN

Total 20: Obtain informed consent. Screen potential subjects by inclusion and exclusion criteria. Perform physical examination and review medical, surgical, and medication histories. Perform a urine pregnancy test for females of reproductive potential. Collect (Day -7 - 0) demographic data including: date of birth, gender, race, ethnicity and tobacco use.

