5 STUDY ENROLLMENT AND WITHDRAWAL

Participants will be recruited from the NYU Winthrop Hospital Wound Care center, inpatient service, and other outpatient surgical services. Consent will be obtained by the principal and sub-investigators of the study.

5.1 Randomization:

Randomization will be performed 1:1 at enrollment. A computer generated randomized block assignment list will be given to the study coordinator. Each block of 2 or 4 subjects will contain an equal number of the two groups: 1) SOC, 2) Promogran+SOC. SAS PROC PLAN will be used to generate this list.

5.2 Inclusion Criteria:

1. Patient ≥ 18 years of age
2. Male or female
3. Patient scheduled to undergo STSG for any reason
4. Patient is able to provide informed consent and has read and signed the IRB-approved informed consent form.

5.3 Exclusion Criteria:

1. Active infection or history of radiation to the donor site
2. Patient has a known sensitivity to Promogran Prisma™ or silver
3. Elevated INR >3.0
4. Insensate at the donor site
5. Chronic narcotic use (>6 months of daily use)
6. Patient is currently pregnant and/or breastfeeding

The target number of enrolled patients will be 20, with 10 patients in the control and treatment groups, respectively. Patients will be allowed to withdraw consent at any time, with no adverse effect on the care received at NYU Winthrop Hospital.

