6 STUDY PROCEDURES AND SCHEDULE

The study will last six weeks. After consent and enrollment, patients in both the control and treatment groups will undergo STSG as scheduled. Promogran will be available in the operating room and applied by the operating surgeon (study or non-study surgeon) directly to the donor site of patients randomized to the treatment group. Patients in the control group will receive SOC dressings per the attending surgeon's clinical judgment. SOC dressings include a primary non-adherent dressing, a secondary gauze and transparent film or tape. The only difference between the two groups is the addition of Prisma in direct contact with the STSG donor site under the primary dressing in the treatment group.

Pain will be patient-reported using the visual analogue/Wong-Baker pain rating scale (VAS), which is reported on a scale from 0-10. Pain will be measured once at each of the following 12 time points: preoperatively, post-operatively (POD 1), and each subsequent postoperative day for ten days. After day 10, pain will be recorded by the assessing clinic provider during the weekly visits, until week six.

Patients will be followed daily while inpatient and weekly while outpatient for six weeks. The number of study visits will be between 6-10. The study visits will be combined with SOC visits and there will

be no study related procedures other than assessing pain at the donor site. Dressings will be changed and wounds assessed according to the standard of care at NYU Winthrop Hospital.

Screening Phase - Week -1 (within 7 days prior to treatment visit)

- Evaluation of eligibility for study inclusion
- Obtain informed consent
- Screening of inclusion/exclusion criteria
- Assign a unique subject identification number (SID).
- Randomize to treatment or control arm
- Perform physical examination and review medical, surgical, and medication histories.
- Perform a urine pregnancy test for females of reproductive potential.
- Collect demographic data including: date of birth, gender, race, ethnicity and tobacco use.
- Give patient pain diary and payment of \$35 patient stipend.

Treatment Phase - Day 0

- Ensure subject remains eligible prior to study product application.
- Confirm negative urine pregnancy test for females of reproductive potential prior to initial product application.
- Application of Prisma to STSG donor site for patients in the treatment group □ Record STSG donor site length and width

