9 STATISTICAL CONSIDERATION

9.1 Sample Size

A pilot study is limited in terms of statistical power due to its small sample size. As a result, no formal power computation was carried out. Proposed sample size (10 patients in each arm, a total of N=20) is obtained from a recruitment and cost feasibility point of view. The main aim of the study is to determine feasibility of the intervention, recruitment, randomization, retention a priori to a large full scale randomized clinical trial. No inferential decision will be made based on p-values; however the direction and size of the effect of the intervention on the outcomes observed will be critical for designing future randomized controlled trial where efficacy of the intervention will be determined.

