14 SCHEDULE OF EVENTS

Activity	Screening Visit [Day -7-0]	Treatment Visit [Day 0]	Follow-Up Phase [Day 1-10]	FollowUp Visit 1 [Day 7±3]	Follow-Up Visit 2 [Day 14±3]	Follow-Up Visit 3 [Day 28±3]	Follow-Up Visit 4 [Day 35±3]	Follow-Up Visit 5 [Day 42 ±3]	Final Visit 6 [Day 49 ±3]
Informed Consent	X								
Eligibility Assessment	X								
Significant Medical, Surgical, Medication History	X								
Baseline demographics: gender, age, height, weight	X								
Pain score at STSG donor site	X	X	X	X	X	X	X	X	X
Randomization		X							
Application of Promogran Prisma™, for intervention group		X							
STSG donor site evaluation and management (SOC dressing, photography, length, width, assessment of appearance)				X	X	X	X	X	X
Closure assessment				X	X	X	X	X	X

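### Time to donor site healing is counted from randomization, which Section 6 allows up to 7 days before the donor wound exists and Section 14 places on Day 0

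*Combined protocol and SAP*

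**What the plan says.** **Start of the clock.** Section 9.4: "Time from randomization to donor site healing will be compared between treatment groups using time to event approach". The Statistical Analysis row of the Protocol Summary agrees: "The secondary endpoint, time from randomization to donor site healing, will be compared between treatment groups". Section 4.2 lists time to complete healing as a secondary aim but names no starting point.

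**When randomization happens.** The sections differ.
- Section 5.1: "Randomization will be performed 1:1 at enrollment". It gives no day count.
- Section 6, under the heading "Screening Phase - Week -1 (within 7 days prior to treatment visit", lists "Randomize to treatment or control arm". The same section puts surgery later: "After consent and enrollment, patients in both the control and treatment groups will undergo STSG as scheduled".
- Section 14 leaves the screening cell of the randomization row empty and marks it only in the column "Treatment Visit [Day 0", the same column as application of the study dressing.

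**When healing is observed.** Section 4.1 defines healing as full epithelialization of the donor site with no drainage. Section 14 schedules closure assessments from Day 7±3 to Day 49±3, with the treatment visit as Day 0.

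No section subtracts the interval between randomization and surgery.

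**The concern.** A donor site cannot heal before it has been harvested. If randomization takes place during screening, the recorded healing time is the sum of two quantities: the wait for surgery and the time the wound took to close. Only the second is of interest. The first reflects operating room scheduling.

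The wait comes before treatment, so it should not favour either arm on average. Two things are at stake: the size of the absolute healing times, and the precision of the comparison in a trial with 10 patients per arm. Both bear on the purpose stated in Section 9.1: "the direction and size of the effect of the intervention on the outcomes observed will be critical for designing future randomized controlled trial". Healing times and their spread are what a later trial would take from this one.

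The endpoint is also not reproducible as written, because the value for a given patient depends on which section the site followed.

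**Working it through.** The plan has no figure to reproduce. Section 9.1 sets N = 20 on recruitment and cost grounds, without a power calculation, and no healing time or SD is given. The check is therefore a comparison of the sections, followed by an illustration of scale.

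**1. Pre-wound time in the clock**

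| Followed | Randomization | Days counted before the wound exists |
|---|---|---|
| Sections 5.1 and 6 | Enrollment, in screening | 0 to 7 |
| Section 14 | Day 0 | 0 |

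Example: a patient heals on Day 14. If randomized on Day −7, the recorded time is 7 + 14 = 21 days. If randomized on Day 0, it is 14 days. For assumed true healing times of 10, 14 and 21 days, a 7-day lead adds 7/10 = 70%, 7/14 = 50% and 7/21 = 33%.

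**2. Chance difference between arms in mean lead**

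Inputs: 10 patients per arm (Section 9.1) and a lead of 0 to 7 whole days (Section 6). The shape of the lead distribution is assumed, because no document gives it.

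- Variance of a whole-day uniform lead on 0 to k: ((k+1)² − 1)/12.
- SD of the difference between two arm means: √(2 × variance/10).
- 95% chance range, by normal approximation: ±1.96 × that SD.

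| Assumed lead | Mean (days) | Variance | SD of difference | 95% range (days) |
|---|---|---|---|---|
| All same-day | 0 | 0 | 0 | 0 |
| Uniform 0–2 | 1.0 | (9−1)/12 = 0.67 | √(2×0.67/10) = 0.37 | ±0.7 |
| Uniform 0–7 | 3.5 | (64−1)/12 = 5.25 | √(2×5.25/10) = 1.02 | ±2.0 |
| Half at 0, half at 7 | 3.5 | 3.5² = 12.25 | √(2×12.25/10) = 1.57 | ±3.1 |

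The last row is the widest spread the window allows, so it is a bound and not an estimate. In 400,000 simulated trials with uniform 0–7 leads, the mean difference was 0.00, the 2.5th and 97.5th percentiles were −2.0 and +2.0 days, and the arms differed by at least 1 day in 36%. With uniform 0–2 leads, that happened in under 1%.

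**3. Effect on the planned test**

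The log-rank test was simulated with 3,000 trials per scenario, 10 per arm, a nominal two-sided 0.05 level and uniform 0–7 leads. Healing times and SDs are assumptions.

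| Mean healing (days), SD | Rejection, clock from surgery | Rejection, clock from randomization |
|---|---|---|
| 14 vs 14, SD 4 | 6.0% | 5.8% |
| 14 vs 10, SD 4 | 55% | 44% |
| 21 vs 14, SD 7 | 55% | 51% |

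The false-positive rate does not change. Some sensitivity is lost, and more is lost when healing times vary little relative to the lead.

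**The case against.** **The defect is conditional.** If Section 14 governs, randomization falls on Day 0 and the clock in Section 9.4 is already right. Screening may also fall on Day 0. This is true, and it is why the lower end of every range above is zero. But Section 6 places randomization in screening and Section 5.1 ties it to enrollment, so a site following them would count the wait.

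**The ±day figures are not on the planned scale.** The analysis is Kaplan-Meier with log-rank, not a difference in means. This also stands: those figures show the size of the disturbance, not how far a Kaplan-Meier median would move. The log-rank simulation addresses the planned test, but only under assumed healing times.

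**Visit spacing is about as coarse.** Section 14 steps from Day 14 to Day 28. If healing falls uniformly between visits (an assumption), detection delay has variance 7²/12 = 4.1 days² for a 7-day gap and 14²/12 = 16.3 for a 14-day gap, against 5.25 for the uniform 0–7 lead. The lead adds to this. With healing rounded up to weekly visits, rejection for 14 vs 10 days was still 47% from surgery and 38% from randomization.

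**Randomization is the conventional origin and keeps every randomized patient.** Moving the origin does not move anyone between arms. A patient who is randomized but never harvested has no donor wound and cannot have the event on either clock. The plan should still say how such patients are reported, since Section 6 rechecks eligibility on Day 0 and the trial is open-label.

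**It is a secondary endpoint in a pilot.** Section 9.1 rules out decisions based on p-values, and the POD 1 pain endpoint is unaffected. If both dates are recorded, the offset can also be removed at analysis. This limits the weight of the point, but the error remains in the text.

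**Conclusion.** The concern holds. Read together, Sections 5.1, 6 and 9.4 count up to 7 days during which healing is impossible, while Section 14 implies none. The conflict rests on the text alone and is certain.

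The practical size is uncertain because the waits are not documented. It runs from nothing, if all patients are randomized on the day of surgery, to a mean lead of 3.5 days and a chance shift between arms of about ±2.0 days under uniform 0–7 waits; the extreme bound is ±3.1 days. There is no expected bias between arms and no inflation of false positives. The harm is overstated absolute healing times, avoidable noise, and an endpoint that two readers could compute differently. It should be corrected, but it does not threaten the primary analysis.

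**What to change.** 1. In Section 9.4 and the Protocol Summary, define the endpoint as time from Day 0 (STSG harvest and dressing application) to donor site healing as defined in Section 4.1. Add the same origin to the aim in Section 4.2.
2. Make Sections 5.1, 6 and 14 state a single randomization point.
3. Keep patients in their randomized arms. State that anyone randomized but not harvested is counted and reported by arm, and has no healing time.

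The change of clock is a matter of wording. Day 0 is already a study visit with its own records, and the closure visits are already numbered from it, so no new data, visits or patients are needed. Settling the randomization point may alter site procedure if practice differs from the text chosen. Under Section 11, the amendment needs IRB approval before it is implemented.

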- Records all pain medications used in postoperative recovery room on POD 0

Follow-Up – Day 1 to 10

- Daily record of pain level in pain journal with the initial record once during 8am to 12pm and prior to each pain medication use
- Record time of any pain medication use
- Record pain of both donor and recipient STSG site

Follow-Up - Weeks 1 to 6 (6 week duration with 1 visit per week)

- Evaluation and record of STSG donor site – photography, length, width
- Record pain level of donor site
- Record any adverse events
- Collection of pain diary and second payment of \$35 stipend.

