9.2 Statistical Analysis Plan

Data will be summarized using descriptive statistics such as mean (standard deviation), median (Interquartile Range) based on the distribution of the continuous variables. Categorical variables will be presented as count (percentage).

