10 SOURCE DOCUMENTS AND ACCESS TO SOURCE DATA/DOCUMENTS

Source data is all information, original records of clinical findings, observations, or other activities in a clinical trial necessary for the reconstruction and evaluation of the trial. Source data are contained in source documents. Examples of these original documents, and data records include: hospital records, clinical and office charts, laboratory notes, memoranda, subjects' diaries or evaluation checklists, pharmacy dispensing records, recorded data from automated instruments, copies or transcriptions certified after verification as being accurate and complete, microfiches, photographic negatives, microfilm or magnetic media, x-rays, subject files, and records kept at the pharmacy, at the laboratories, and at medico-technical departments involved in the clinical trial. It is acceptable to use CRFs as source documents. If this is the case, it should be stated in this section what data will be collected on CRFs and what data will be collected from other sources.

The study case report form (CRF) is the primary data collection instrument for the study. All data requested on the CRF must be recorded. All missing data must be explained. If a space on the CRF is left blank because the procedure was not done or the question was not asked, write "N/D". If the item is not applicable to the individual case, write "N/A". All entries should be printed legibly in black ink. If any entry error has been made, to correct such an error, draw a single straight line through the incorrect entry and enter the correct data above it. All such changes must be initialed and dated. DO NOT ERASE OR WHITE OUT ERRORS. For clarification of illegible or uncertain entries, print the clarification above the item, then initial and date it.

Access to study records will be limited to IRB-approved members of the study team. The investigator will permit study-related monitoring, audits, and inspections by the IRB/EC, the sponsor, government regulatory bodies, and University compliance and quality assurance groups of all study related documents (e.g. source documents, regulatory documents, data collection instruments, study data etc.). The investigator will ensure the capability for inspections of applicable study-related facilities (e.g. pharmacy, diagnostic laboratory, etc.).

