12 DATA HANDLING AND RECORD KEEPING

Data collection is the responsibility of the clinical trial staff at the site under the supervision of the site PI. The investigator is responsible for ensuring the accuracy, completeness, legibility, and timeliness of the data reported.

All source documents should be completed in a neat, legible manner to ensure accurate interpretation of data. Black ink is required to ensure clarity of reproduced copies. When making changes or corrections, cross out the original entry with a single line, and initial and date the change. DO NOT ERASE, OVERWRITE, OR USE CORRECTION FLUID OR TAPE ON THE ORIGINAL.

Copies of the electronic CRF (eCRF) will be provided for use as source documents and maintained for recording data for each participant enrolled in the study. Data reported in the eCRF derived from source documents should be consistent with the source documents or the discrepancies should be explained and captured in a progress note and maintained in the participant's official electronic study record.

Clinical data (including AEs, concomitant medications, and expected adverse reactions data) and clinical laboratory data will be entered into a local database kept and maintained at NYU Winthrop Hospital by the Wound Care team. Access to the data system includes password protection and internal quality checks, such as automatic range checks, to identify data that appear inconsistent, incomplete, or inaccurate. Clinical data will be entered directly from the source documents.

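### Section 9.4 treats use of pain medication and amount of pain medication as one endpoint and compares it by Fisher's exact test, with no medication cut-points, no stated analysis window and no between-arm estimate with an interval

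*Combined protocol and SAP*

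**What the plan says.** Section 4.2 lists, as the fifth of six secondary aims, a comparison of reduced use of narcotics and other pain medications. It gives no unit, threshold or period.

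Section 9.4 turns this into an analysis and names Fisher's exact test to complete this clause: "percent use of narcotics and other pain medication (ie amount of medication used) and percent of granulation will be compared between groups using". Percent healed is in the same sentence and gets the same test. Granulation has four bands defined in Section 4.2; medication has none.

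Section 6 sets the collection periods. On the day of surgery: "Records all pain medications used in postoperative recovery room on POD 0". For Days 1 to 10, the diary item is: "Daily record of pain level in pain journal with the initial record once during 8am to 12pm and prior to each pain medication use". A further item for the same days is: "Record time of any pain medication use". Section 9.4 does not say which of these periods is analysed.

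Section 9.2 plans mean (SD) or median (IQR) for continuous variables and counts with percentages for categorical ones. Section 9.4 adds nominal p-values. Section 9.1 says that no inferential decision will rest on p-values, but that "the direction and size of the effect of the intervention on the outcomes observed will be critical for designing future randomized controlled trial".

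**The concern.** The share of patients who took any narcotic and the quantity each patient took are different variables and need different analyses. Section 9.4 gives one as the explanation of the other and assigns a test for categories. Two competent analysts could follow the sentence and report different results.

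Under the yes/no reading the test fits, but it does not see a reduction among patients who all take something after surgery. Under the amount reading the test needs categories, and the plan leaves them to be chosen later.

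Two things are at stake. First, this pilot's product is the direction and size of effects, and neither reading of the sentence delivers a size with its uncertainty. Second, the trial is open-label with POD 1 pain as the primary endpoint, and a pain score is hard to interpret without knowing how much analgesic preceded it. Similar pain with less narcotic would be a benefit, and a yes/no comparison could miss it.

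**Working it through.** **The plan's own figure.** N=20 (10 + 10) is set by recruitment and cost in Section 9.1, with no power computation, so there is no formula to reproduce. The check is a reading of the text plus an illustration at 10 per arm. All amounts, spreads and non-user rates below are assumptions.

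**Step 1: data.** Two non-users per arm. The eight users' amounts are the mid-quantiles of a lognormal with log-SD 0.6, with median 100 units (control) or 50 (treatment), rounded. Every user's amount is thus about halved.

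- Control: 0, 0, 40, 59, 75, 91, 110, 134, 170, 251
- Treatment: 0, 0, 20, 29, 37, 45, 55, 67, 85, 126

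**Step 2: yes/no reading.** Any use is 8/10 v 8/10. Fisher p=1.00; risk difference 0, Newcombe 95% CI -34 to +34 percentage points. The halving is invisible.

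**Step 3: amount reading with a cut.** Two-sided Fisher on patients above the cut:

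| Cut (units) | Treatment | Control | p |
|---|---|---|---|
| 25 | 7/10 | 8/10 | 1.00 |
| 50 | 4/10 | 7/10 | 0.37 |
| 75 | 2/10 | 5/10 | 0.35 |
| 100 | 1/10 | 4/10 | 0.30 |
| 125 | 1/10 | 3/10 | 0.58 |

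The data are the same in every row; only the cut changes.

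**Step 4: amount reading without a cut.** The test can be computed on raw values. With 20 distinct amounts and 10 per arm, every table with the same margins has the same probability, so p=1 whatever the data. Here the only tie is the four zeros, split 2 v 2. That is the most probable split, so again p=1.

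**Step 5: what Section 9.2 would show.** If amount is summarised as continuous, the medians are (75+91)/2 = 83 and (37+45)/2 = 41. The crude difference is 41 - 83 = -42 units, with no interval.

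**Step 6: an analysis suited to an amount.** The Hodges-Lehmann estimate is the median of the 10 x 10 = 100 pairwise differences (treatment minus control): -40 units. The 95% limits are the 24th and 77th ordered differences: -103 and 16. Rank-sum p=0.14 (tie-corrected).

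**Step 7: sensitivity to the assumptions.** Simulation, 10,000 trials per setting, control users' median 100 and treated users' median 50. Entries are the median estimate and median 95% limits.

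| Non-users | Log-SD | Difference (95% limits) |
|---|---|---|
| None | 0.6 | -46 (-100 to -7) |
| None | 0.8 | -44 (-119 to 5) |
| 20%, entered as zero | 0.6 | -39 (-98 to 15) |
| 20%, entered as zero | 0.8 | -33 (-109 to 24) |

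Coverage of the true median pairwise difference was 0.946 to 0.953. In the same settings the any-use Fisher test gave p=1 in every trial with no non-users, and in 60 to 61% of trials with 20% non-users.

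**The case against.** The strongest reply is that little is lost. The plan intends to describe as well as compare, and Section 9.2 would give a median or mean per arm if amount is treated as continuous, so direction and crude size would be visible. This stands. A reader might infer that only p-values would be reported, and the documents do not support that. What is missing is a between-arm estimate with an interval, and a statement of which variable is being summarised. The lack of intervals is also not peculiar to this endpoint: Sections 9.3 and 9.4 plan none anywhere.

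The illustration changes no conclusion. Every Fisher p is at least 0.30, the rank-sum p is 0.14, and the interval of -103 to 16 includes no effect. Section 9.1 bars decisions on p-values in any case. This also stands: the example shows that the output depends on an unstated choice, not that a significant result is being missed.

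Three stronger readings are tempting and go too far:

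- That Fisher's test is invalid or cannot be run. It is valid for yes/no use and for granulation, and on raw amounts it runs but says nothing.
- That no period is defined. Section 6 bounds the choice to the POD 0 recovery room and Days 1 to 10; Section 9.4 just does not pick.
- That an amount cannot be derived because, for Days 1 to 10, only the time of use is listed. The diary form is not in the documents. Section 12 refers to "Clinical data (including AEs, concomitant medications, and expected adverse reactions data" as database content, and Section 10 names "evaluation checklists, pharmacy dispensing records" among its examples of source documents. Drug and dose may be held there. This is something to confirm, not an error.

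**Conclusion.** The point holds for the medication comparison in Section 9.4. The sentence equates two variables, and the named test serves only one of them. For the other it is either uninformative (uncategorised) or dependent on a cut that is not pre-specified: p from 0.30 to 1.00 on one assumed dataset in which users' amounts are halved. A crude difference could be read from the Section 9.2 summaries, but no interval is planned, and this sits poorly with the weight that Section 9.1 puts on effect size.

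The textual finding rests on no assumption. The figures rest on assumed lognormal amounts, an assumed halving and assumed non-user rates, and show only how far the result can move. At 10 per arm any interval will be wide, and the proposed analysis does not promise a significant result. The severity is modest: one of six secondary aims in a pilot with nominal p-values. It is still worth correcting, because the analysis as written is not reproducible and the correction is cheap.

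**What to change.** Replace the medication part of the Section 9.4 sentence with two endpoints:

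- **(a) Any use**, yes/no, separately for narcotics and for other analgesics: Fisher's exact test with a risk difference and 95% CI.
- **(b) Narcotic amount per patient** in one pre-specified common unit: rank-sum test (already the planned test for POD 1 pain in Section 9.3) with a Hodges-Lehmann difference in that unit and 95% CI. Enter zero only where no use occurred. A missing drug or dose is missing; report the number with data per arm.

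Report (b) with the same estimate and interval for two stated windows: POD 0 up to the POD 1 pain record, and Days 1 to 10. The first is the one that helps interpret the primary endpoint, because most of Days 1 to 10 falls after that score. Other analgesics can be analysed as number of uses per patient in the same way; do not pool an amount across drug classes.

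Confirm that the diary, chart or concomitant-medication record holds drug and dose for Days 1 to 10, and use between leaving recovery and Day 1. Add the fields only if they are absent. Patients already enrolled without them would contribute counts of uses or chart data.

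Optional: compare the ordered granulation bands with a test that uses their order (rank-sum or exact linear-by-linear) at a named visit.

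Cost: one rewritten sentence, a form check, a few more secondary summaries, possibly a slight diary burden, and IRB review of the amendment (Section 11). No extra visits or patients.

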4.2 Study Endpoints

The primary aim of this feasibility study is to evaluate if using Promogran in addition to SOC will improve the pain score compared to SOC alone. Specifically, we would like to detect a clinically meaningful difference in pain score (≥ 2 points on the pain scale) between the treatment and control arms on postoperative day (POD) 1.

Secondary aims include:

1. Describe and compare the percent of patients healed between treatment groups
2. Describe and compare weekly surface area between treatment groups
3. Compare time to complete donor site healing between treatment groups

4. Describe and compare adverse events between groups
5. Describe and compare decreased use of narcotics and other pain medications between groups
6. Describe and compare percent of granulation tissue at the donor site between treatment groups.
Granulation will be reported in quartiles (0-25%, 26-50%, 51-75%, and 76-100%).

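### Granulation is reported in four ordered bands but compared with Fisher's exact test, which is valid but ignores the order and gives no direction or size of effect (minor, secondary endpoint)

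*Combined protocol and SAP*

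**What the plan says.** Granulation is the last of six secondary aims in Section 4.2: "Describe and compare percent of granulation tissue at the donor site between treatment groups". The same item fixes the scale: "Granulation will be reported in quartiles (0-25%, 26-50%, 51-75%, and 76-100" percent. These are four ordered categories.

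Section 9.4 states the comparison: "percent of granulation will be compared between groups using" Fisher's exact test. It names no ordinal version, no scores, no effect estimate and no visit.

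The sample is small by design. Section 9.1 gives "Proposed sample size (10 patients in each arm, a total of N=20" and adds that "no formal power computation was carried out". It also says that p-values will not drive decisions, and that the direction and magnitude of the observed effects are what the next trial needs. Section 9.2 summarises categorical variables as counts with percentages.

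On data collection, the weekly list in Section 6 has photographs, length and width. The donor-site row of Section 14 reads "photography, length, width, assessment of appearance" after the dressing. Neither uses the word granulation.

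**The concern.** Fisher's test on a 2×4 table asks whether the two arms differ in any way across four unlabelled categories. A steady move of one arm toward higher bands counts the same as scatter with no pattern. The order of the bands, which is what makes the endpoint directional, is not used.

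The plan already contains a method that uses order: Section 9.3 compares the POD 1 pain score with a Wilcoxon rank-sum test.

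At stake is how informative one secondary comparison is. Section 9.4 will print a nominal p-value for granulation with no estimate beside it, while Section 9.1 says that the estimate is what matters.

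**Working it through.** The plan states no power, effect size or significance level for granulation, so there is no figure of its own to reproduce.

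**Inputs from the documents.** Four ordered bands (Section 4.2); Fisher's exact test (Section 9.4); 10 patients per arm (Section 9.1); allocation 1:1, "Randomization will be performed 1:1 at enrollment" (Section 5.1).

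**Assumptions not in the documents.** Two-sided 5% level; all 20 patients assessed at one common visit; the band distributions below.

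**Method.** Every 2×4 table with 10 per arm was enumerated. Given column totals t₁ to t₄, a table with a₁ to a₄ patients in one arm has probability ∏C(tⱼ, aⱼ) / C(20, 10). The Fisher (Freeman-Halton) p-value sums the probabilities of all tables no more likely than the observed one. The exact Wilcoxon p-value sums those of all tables whose midrank sum lies at least as far from its expectation, 10 × 10.5 = 105.

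**One table by hand.** Control 4/3/2/1, treated 1/2/3/4, lowest to highest band. Each column total is 5.
- Fisher: table probability = 5 × 10 × 10 × 5 / 184,756 = 2,500 / 184,756 = 0.0135. Summing all tables no more likely gives p = 0.459.
- Wilcoxon: midranks are 3, 8, 13, 18. Control rank sum = 4×3 + 3×8 + 2×13 + 1×18 = 80; treated = 3 + 16 + 39 + 72 = 130. Each is 25 from 105; exact p = 0.077.
- Mann-Whitney probability (treated site in the higher band, ties one half) = (130 − 55) / 100 = 0.75. This is a direction and a size; Fisher's test has no counterpart on four bands.

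A second table, control 4/3/2/1 against treated 0/2/3/5, gives Fisher 0.097 and Wilcoxon 0.014.

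**Order check.** For 5/3/1/1 against 1/2/4/3, Fisher gives 0.161 and Wilcoxon 0.031. With the bands shuffled, Fisher stays at 0.161 and Wilcoxon moves to 0.502.

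**Exact power, 10 per arm.**

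| Assumed difference | Control | Treated | Fisher | Wilcoxon |
|---|---|---|---|---|
| None (size) | .25/.25/.25/.25 | same | 4.3% | 4.0% |
| Mild shift | .30/.30/.25/.15 | .15/.25/.30/.30 | 10% | 15% |
| Mostly top band | .10/.10/.20/.60 | .02/.03/.05/.90 | 17.5% | 19.0% |
| Reversed mix | .40/.30/.20/.10 | .10/.20/.30/.40 | 33.5% | 49.5% |
| More extreme | .40/.30/.20/.10 | .05/.15/.30/.50 | 53.6% | 71.7% |
| Non-monotone | .40/.10/.10/.40 | .10/.40/.40/.10 | 61% | 7% |

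**Proportional-odds shifts from three assumed control distributions.** Odds ratio 3: Fisher 14–15%, Wilcoxon 18–22%. Odds ratio 5: 25–30% and 33–43%. Odds ratio 8: 38–46% and 47–64%. Odds ratio 12: 48–63% and 57–79%. Within a given distribution, the gain is about 5 to 18 percentage points.

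**The case against.** The case for leaving the plan alone has four parts.

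- **Fisher's test is valid and p-values decide nothing.** It holds its size, and Section 9.1 rules out decisions based on p-values. This stands: the point is about efficiency and reporting, not error. It also cuts the other way, because the direction and size that Section 9.1 asks for are not specified for granulation anywhere in Section 9.
- **A reader might infer that a consistent shift would go unseen.** The documents do not support that. Section 9.2 puts the band counts by arm in the report, where a move from 4/3/2/1 to 1/2/3/4 is plain. Only the p-value is blind to it.
- **A reader might infer that the loss of power is large.** That holds only for large assumed shifts. For the mild shift the gain is about 5 points, and with most patients in the top band it is 1.5. The documents give no granulation distribution to choose between these. For a non-monotone difference Fisher is clearly better. The documents also never say which direction of granulation is favourable: Section 4.1 defines healing by epithelial cover and absence of drainage.
- **A reader might infer that the band is never collected, since Sections 6 and 14 do not name it.** That does not follow. The appearance assessment, the photographs or the case report form, which is not among the documents, could each supply it. What stands is missing detail.

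**Conclusion.** The test does not fit the scale, and the consequence is minor. Fisher's test on the four bands is valid but discards their order and gives no estimate. An exact rank test holds the same size (about 4%) and had more power in every one-way shift examined, by 1.5 to 18 percentage points. It had less in the non-monotone case (7% against 61%). At 10 per arm, power is low with either test unless the shift is large. So the more useful gain is the effect estimate with its interval, which serves the purpose stated in Section 9.1.

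These sizes rest on assumed band distributions, a two-sided 5% level and complete data at a single visit. The finding that Fisher's test ignores order rests on none of them. The primary endpoint is not affected.

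**What to change.** In Section 9.4:
- Name one follow-up visit for the granulation comparison. Up to six follow-up visits could supply a band, and without a named visit no single test can be run. Define the visit by day as well as number: Section 6 has weekly visits in weeks 1 to 6, while Section 14 places its six visits at days 7, 14, 28, 35, 42 and 49. The two must be reconciled first.
- Compare the bands at that visit with an exact Wilcoxon rank-sum test.
- Report the Mann-Whitney probability, ties counted one half, with a 95% confidence interval, beside the band counts by arm.
- Keep Fisher's test for binary endpoints.

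As a clarification, list the granulation band in the weekly procedures of Section 6 and the donor-site row of Section 14, so that its source is explicit.

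The cost is a few lines of analysis-plan wording, plus a form field if the case report form lacks one. No visit or procedure is added. The statistical price is insensitivity to non-monotone differences, which the tabulated counts would still show.
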